All patients will have an EOS visit 30 (± 7) days following their last administration of HGT-1410 (ie, Month 102). The EOS procedures will include standard clinical laboratory tests (serum chemistry, hematology, and urinalysis) in CSF and blood, protocol specific laboratory testing (eg, anti-rhHNS antibody testing), neurodevelopmental testing, child health questionnaires, and MRI.

Use of concomitant medications, therapies, and procedures will be recorded and AEs will be monitored.

All patients will be contacted by telephone or will have a visit for a Final Safety Follow-up, to be conducted at 30 (± 7) days after the EOS visit (ie, Month 103) to collect updated information on AEs and concomitant medications, therapies, and procedures.

It is anticipated that the IDDD will be used to obtain CSF samples and to deliver administrations of HGT-1410. However, if a patient's IDDD appears nonfunctional or if its use is precluded on a scheduled day of dosing, site personnel will refer to the operations manual (for PORT-A-CATH) or the IDDD Manual (for SOPH-A-PORT), which describes the investigation and management of IDDD-related issues. This will include possible partial revision or complete replacement of the IDDD. As noted above, a maximum of 2 partial revisions and/or complete replacements can occur in any 6 month period. If revision or replacement of the IDDD cannot be scheduled in time to avoid a delay of the next scheduled dose of HGT-1410, or if the patient experiences more than 2 IDDD malfunctions in a 6 month period (including participation in study HGT-SAN-055), HGT-1410 will be administered via lumbar puncture (LP).

If there are medical contra-indications to the re-implantation of a new device, or if the patient so desires, repeat monthly lumbar punctures may be considered as an alternative way of delivering the study drug and obtaining CSF samples under limited circumstances. If no safety risks are identified by the investigator, up to 12 consecutive lumbar punctures may be performed across the studies HGT-SAN-055 and HGT-SAN-067. Once a patient has reached the maximum of 12 consecutive lumbar punctures, a new IDDD may be re-implanted for subsequent dosing, unless, in the opinion of the investigator and medical monitor, assessment of risk/benefit favors continued dosing via lumbar puncture.

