It is anticipated that the IDDD will be used to obtain CSF samples and to administer HGT-1410. However, if a patient's PORT-A-CATH IDDD appears nonfunctional or if its use is precluded on a scheduled day of dosing, site personnel will refer to the PORT-A-CATH Instructions for Use (IFU), which describes the investigation and management of IDDD-related issues with this device. This will include possible partial revision or complete replacement of the PORT-A-CATH IDDD with a SOPH-A-PORT IDDD. For malfunctions involving the SOPH-A-PORT Mini S, site personnel will refer to the SOPH-A-PORT IFU. For either IDDD, a maximum of 2 partial revisions and/or complete replacements are permitted in any 6 month period (including participation in study HGT-SAN-055). If a revision or replacement of the IDDD cannot be scheduled in time to avoid a delay of the next scheduled dose of HGT-1410, or if the patient experiences more than 2 IDDD malfunctions in a 6 month period, HGT-1410 will be administered via lumbar puncture (LP). If implantation of a replacement IDDD is not possible, investigational drug may be administered by LP for a maximum of 12 successive monthly doses. At that point, a safety discussion needs to take place between the investigator and the sponsor to determine the risk/benefit of further dosing by LP.

If there is no significant safety risk in the opinion of the investigator, a non-functional IDDD may be left in situ for up to 3 months.

Patients who discontinue or are withdrawn before receiving 3 monthly IT injections will not have to undergo the EOS evaluations but will have their IDDD removed.

If a patient discontinues, or withdraws from the study, or the study is stopped by the sponsor, the IDDD will be removed as part of the EOS Procedures.

An overview of the study appears in the Schedule of Events ([Appendix 1](#)).

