4.2 Rationale for Study Design and Control Group

The original study, Study HGT-SAN-055, is an ongoing Phase I/II safety and ascending dose ranging study of IT administration of HGT-1410 via an IDDD, in patients 3 years of age and older with MPS IIIA and early cognitive impairment. This extension study is proposed to continue evaluation of the effects of IT HGT-1410 administration on long-term safety and clinical outcomes for patients who completed Study HGT-SAN-055 and elected to continue treatment with HGT-1410 in the HGT-SAN-067 study.

In order to traverse the blood-brain barrier, Shire is evaluating HGT-1410 delivered directly to the CNS using an IDDD. The advantage of using an IDDD is that it obviates the need for multiple lumbar punctures for drug delivery. Drug products will be administered through this port or, if the IDDD is non functional, via lumbar puncture.

If patients in the study require revision and/or replacement of the PORT-A-CATH IDDD, it will be removed and replaced with the SOPH-A-PORT Mini S device at a time judged appropriate by the investigator.

SOPH-A-PORT Mini S revision, implantation or explantation will be performed at the main site. However, if in the opinion of the investigator, emergency removal is clinically necessary, device explantation may be performed at the patient's local site.

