In the event of IDDD malfunction, CSF collection and study drug administration may be performed via LP (see Section 6.3.2). The investigation and management of a malfunctioning IDDD is detailed in the PORT-A-CATH or SOPH-A-PORT IFUs. Partial or complete replacement of the IDDD may be necessary (only permitted twice in a 6-month period, including the time a patient was in study HGT-SAN-055), and will require scheduling of the appropriate procedure. The definitive diagnosis of the cause of IDDD failure may not be possible until the time of exploratory surgery. Surgery will take place at the earliest convenience, so the patient may remain on, or as close as possible to their treatment schedule.

6.3.2 Administration of HGT-1410 via Lumbar Puncture Guidance Concerning Performance of Lumbar Puncture for Study Drug Administration and Cerebrospinal Fluid Sample Collection

It is intended that the IDDD will be used to deliver all IT injections of study drug and to obtain CSF samples. If the IDDD appears to be nonfunctional, or if its use is precluded on a scheduled day of dosing, site personnel will refer to the IDDD manual (s), which provides details on the investigation and management of any IDDD-related issues. This may include possible partial revision or complete replacement of the IDDD as indicated. If the nonfunctional IDDD is a PORT-A-CATH device, then it will be replaced by a SOPH-A-PORT Mini S device.

If there are medical contra-indication to the re-implantation of a new device, or if the patient so desires, repeat monthly lumbar punctures may be considered as an alternative way of delivering the study drug and obtaining CSF samples under limited circumstances. If no safety risks are

identified by the investigator, up to 12 consecutive lumbar punctures may be performed across studies HGT-SAN-055 and HGT-SAN-067. Once a patient has reached the maximum of 12 consecutive lumbar punctures, a new IDDD will be re-implanted for subsequent dosing, unless, in the opinion of the investigator and medical monitor, assessment of risk/benefit favors continued dosing via lumbar puncture.

Continued treatment via repeat lumbar puncture beyond the stipulated 12 consecutive monthly doses can be considered only in individual cases of patients where this treatment is very well tolerated and the investigator has not identified any safety concerns associated with repeat lumbar puncture and repeat sedation/anesthesia.

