7.15 Dispensing Study Drug

A visual examination of both the port and catheter track will be performed before each IT injection.

HGT-1410 will be administered IT by means of an IDDD (or via LP if necessary) to patients on Day 2 (± 2 days) of Week 1 of each treatment month.

The patient may be sedated for this procedure. HGT-1410 will be administered through an appropriately sized syringe (see the Pharmacy Manual). If the IT space is not accessible via the IDDD, HGT-1410 may be administered via LP. See Section 6.3.2 for details.

For the Soph-A-Port Mini S, a 22-gauge Huber non-coring needle is to be used for access to the implanted port; standard hypodermic needles would damage the septum and may cause leakage. If no needle-free connector is present, either a stopcock or the Huber needle infusion set's clamp is to be used to prevent CSF backflow and to mitigate the risk of air entering the system. It is possible to use other brands of Huber non-coring needles, provided that their specifications are identical to that of the Huber needle supplied by Sophysa in the SOPH-A-PORT Mini S (22G).

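### The mandatory switch to lumbar-puncture dosing in 4.1 and the synopsis is counted in malfunctions, a term that 7.22.2.2 defines as events needing no revision

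*Protocol*

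**What the plan says.** Section 4.1 and the synopsis (Study Design) each give two triggers for LP dosing, joined by *or*. The first applies when a revision or replacement cannot be scheduled in time for the next dose. The second is a count. In 4.1 it reads "if the patient experiences more than 2 IDDD malfunctions in a 6 month period, HGT-1410 will be administered via lumbar puncture". The synopsis has "if the patient experiences more than 2 IDDD malfunctions in a 6 month period (including participation in study HGT-SAN-055" as the condition, with the same mandatory consequence. The count clause says nothing about the state of the port at the dosing visit.

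The 4.1 paragraph opens with a port that "appears nonfunctional or if its use is precluded on a scheduled day of dosing". Just before the LP sentence it sets the limit that "a maximum of 2 partial revisions and/or complete replacements are permitted in any 6 month period".

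The other places that bear on the point are:

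- **4.2:** "Drug products will be administered through this port or, if the IDDD is non functional, via lumbar puncture".
- **6.3.1:** "In the event of IDDD malfunction, CSF collection and study drug administration may be performed via LP".
- **6.3.2:** on medical contraindication to a new device, or "if the patient so desires, repeat monthly lumbar punctures may be considered as an alternative way".
- **7.15:** dosing is by the IDDD, with LP where necessary, and "If the IT space is not accessible via the IDDD, HGT-1410 may be administered via LP".
- **7.22.2.2 and 7.22.2.3:** a malfunction is underperformance that calls for no revision; a failure is irreversible and calls for revision or removal.
- **7.13.4:** a malfunction is declared when the device prevents a full scheduled dose, and becomes a failure if it is irreversible and needs surgery.

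**The concern.** A compulsory change of dosing route should rest on a term that identifies the intended patients. Here it rests on a count of events that, by the protocol's own definition, leave the device in place without surgery. A child whose port has blocked three times and recovered each time meets the trigger. The sentence then requires LP, and it sets no point at which port dosing resumes.

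What is at stake is avoidable exposure. Section 7.22.1.4 lists infection, meningitis, spinal fluid leakage and nerve damage among the risks of LP, and says that anesthesia, with its own risks, may be needed. Section 4.2 gives avoidance of repeated LP as the advantage of the implanted device. A site that continues to use a recovered port departs from a mandatory sentence; a site that obeys the sentence gives up that advantage. No estimate, interval or sample size is involved.

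**Working it through.** The plan has no figure of its own to reproduce on this point. The check is to apply the sentences to two cases.

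**Inputs.** The trigger is more than 2 malfunctions in 6 months (4.1, synopsis). The limit is 2 revisions or replacements in 6 months (4.1). The definitions are in 7.22.2.2, 7.22.2.3 and 7.13.4. The conditions for LP are in 4.2 and 7.15.

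**Case A: three reversible events within 6 months, port working at the next dose.**

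1. Each event needs no revision, so each is a malfunction under 7.22.2.2. If each also blocked a scheduled dose, each is a malfunction under 7.13.4 as well.
2. The count is 3, and 3 > 2, so the trigger is met.
3. Revisions used: 0 of 2.
4. Section 4.1 and the synopsis, read literally, require LP.
5. Section 4.2 points to the port, because the device is functional. So does 7.15, because LP is not necessary.

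**Case B: two failures, each revised, then a third failure within the same 6 months.**

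1. Each event needs revision, so each is a failure under 7.22.2.3 and falls outside the definition in 7.22.2.2. Counted by that definition, malfunctions number 0, and the trigger is not met.
2. Under 7.13.4, a failure found at dosing is first declared a malfunction. On that usage the count is 3 and the trigger is met.
3. Revisions used: 2 of 2. No further revision is permitted.
4. LP is clearly appropriate. It would probably be reached anyway, through the scheduling trigger or through 4.2.

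The count therefore catches Case A under either definition, and catches Case B under only one of them. Case B is the one that the preceding sentence, with its limit of 2 revisions, leads up to.

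**Evidence of intent.** The X-ray text in 4.1 and the synopsis allows 3 X-rays for each malfunction episode together with the revision that follows it. The synopsis derives its ceiling of 6 X-rays in 6 months from the limit of 2 revisions: 2 × 3 = 6. In that text one malfunction goes with one revision. On that usage, more than 2 malfunctions means a third episode after the revision allowance is spent, which is Case B.

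**The case against.** The strongest reply is that context supplies the missing condition. The paragraph opens with a port that is nonfunctional or cannot be used on the dosing day. Section 6.3.2, the dedicated LP section, states the intention that the IDDD deliver every injection and opens its exceptions with the same condition. The trigger directly follows the limit of 2 revisions, and the X-ray text pairs each malfunction with a revision. A reader who takes all of this together would reach Case B. That argument stands as to probable intent. It does not repair the sentence: the opening condition introduces referral to the device instructions and is not repeated in the LP sentence, and the word used is a defined term with the opposite content.

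A reader might also infer a direct conflict between *will* in 4.1 and *may* in 6.3.1 and 7.15. The documents do not support that for a recovered port. The permission in 6.3.1 covers a current malfunction, including a first one, and that in 7.15 covers an inaccessible intrathecal space. A general permission and a specific rule for repeated events can stand together. The mismatch for a working port is with 4.2 and with the necessity condition in 7.15. Of these, 4.2 is rationale text and does not say that LP is reserved for non-functional devices, and 6.3.2 also lets LP be considered at the patient's wish.

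Finally, device management is left to instructions and manuals that are not part of the document. They may settle practice at sites, so divergent handling is a possibility and has not been shown.

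**Conclusion.** The point holds as a wrong defined term in an operative dosing rule. Under 7.22.2.2, the mandatory LP trigger is met by three reversible events with a working port and 0 of 2 revisions used, contrary to 4.2 and 7.15. A reader might conclude that the sponsor meant LP for children whose ports work. The text does not show this: the opening condition, the revision limit and the X-ray pairing all point to a third event that can no longer be revised.

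The conclusion assumes that sites read malfunction as section 7.22.2.2 defines it, or as 7.13.4 does for events that later reverse. The weight is minor: it concerns patient safety through route of dosing, and no statistical figure is affected. Section 5.1 plans at most 12 patients. The document gives no malfunction rate, so neither the number of children affected nor the number of extra punctures can be derived.

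**What to change.** In 4.1 and the synopsis, keep the scheduling trigger and replace the count trigger with:

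> or if the limit of 2 revisions/replacements in a 6 month period has been reached and the IDDD is non-functional or its use is precluded on the scheduled dosing day, HGT-1410 will be administered via LP

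Keep the statement that time in HGT-SAN-055 counts towards the 6 months. Replacing malfunctions with failures would be a smaller change and would remove the wrong term. It would still not tie LP to the state of the port on the dosing day, or say when port dosing resumes.

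The cost is one clause in two places, with no added procedure and no change to any analysis. A child with repeated reversible malfunctions would no longer be moved to LP by the count alone; the existing permissions in 6.3.1, 6.3.2 and 7.15 are untouched.

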4.2 Rationale for Study Design and Control Group

The original study, Study HGT-SAN-055, is an ongoing Phase I/II safety and ascending dose ranging study of IT administration of HGT-1410 via an IDDD, in patients 3 years of age and older with MPS IIIA and early cognitive impairment. This extension study is proposed to continue evaluation of the effects of IT HGT-1410 administration on long-term safety and clinical outcomes for patients who completed Study HGT-SAN-055 and elected to continue treatment with HGT-1410 in the HGT-SAN-067 study.

In order to traverse the blood-brain barrier, Shire is evaluating HGT-1410 delivered directly to the CNS using an IDDD. The advantage of using an IDDD is that it obviates the need for multiple lumbar punctures for drug delivery. Drug products will be administered through this port or, if the IDDD is non functional, via lumbar puncture.

If patients in the study require revision and/or replacement of the PORT-A-CATH IDDD, it will be removed and replaced with the SOPH-A-PORT Mini S device at a time judged appropriate by the investigator.

SOPH-A-PORT Mini S revision, implantation or explantation will be performed at the main site. However, if in the opinion of the investigator, emergency removal is clinically necessary, device explantation may be performed at the patient's local site.

4.3 Study Duration and Dates

The study duration allows patients who completed Study HGT-SAN-055 and elected to continue treatment with HGT-1410 in Study HGT-SAN-067 to receive treatment with HGT-1410 up to 8 years.

5 STUDY POPULATION SELECTION

5.1 Study Population

Patients who have completed all study requirements in Study-HGT-SAN-055 and who elected to continue HGT-1410 treatment will be eligible to participate; a maximum of 12 patients are planned for this study.

5.2 Inclusion Criteria

Each patient must meet the following criteria to be considered eligible for enrollment in this study.

1. The patient must have completed Study HGT-SAN-055 and, in the opinion of the investigator, have no safety or medical issues that contraindicate participation.
2. The patient, patient's parent(s) or legally authorized representative(s) has voluntarily signed an Institutional Review Board/Independent Ethics Committee-approved informed consent (and assent, if applicable) form after all relevant aspects of the study have been explained and discussed with them. Informed consent/assent must be obtained prior to any study specific procedures.
3. The patient has received at least 5 of the 6 planned infusions of HGT-1410 in the HGT-SAN-055 study.
4. The patient must be medically stable, in the opinion of the investigator, to accommodate the protocol requirements, including travel, assessments, and IDDD surgery (if necessary for replacement purposes), without placing an undue burden on the patient/patient's family.

5.3 Exclusion Criteria

Patients will be excluded from the study if there is evidence of any of the following:

1. The patient has experienced an adverse reaction to study drug in Study HGT-SAN-055 that contraindicates further treatment with HGT-1410.
 2. The patient has a known hypersensitivity to the active ingredient or any excipients in HGT-1410 drug product.
 3. The patient has significant non-MPS IIIA related central nervous system impairment or behavioral disturbances that would confound the scientific integrity or interpretation of study assessments, as determined by the investigator.
 4. The patient has MPS IIIA behavioral-related issues, as determined by the investigator, which would preclude performance of study neurocognitive and developmental testing procedures.
 5. The patient is pregnant, breast feeding, or is of childbearing potential who will not or cannot comply with the use of an acceptable method of birth control, such as condoms, barrier method, oral contraception, etc.
 6. The patient has any known or suspected hypersensitivity to anesthesia or is thought to have an unacceptably high risk for anesthesia due to airway compromise or other conditions.
 7. The patient has a history of a poorly controlled seizure disorder.
-

8. The patient is currently receiving psychotropic or other medications, which in the investigator's opinion, would be likely to substantially confound test results and the dose and regimen of which cannot be kept constant throughout the study.
9. The patient cannot sustain absence of aspirin, non-steroidal medications, or medications that affect blood clotting within 1 week prior to a relevant study-related procedure (eg, device re-implantation if applicable), or has ingested such medications within 1 week before any procedures in which any change in clotting activity would be deleterious.
10. The patient has received treatment with any investigational drug (other than HGT-1410) intended as a treatment for MPS IIIA within the 30 days prior to, during the study, or is currently enrolled in another study that involves an investigational drug or device (screening through safety follow-up contact).
11. The patient has received a hematopoietic stem cell or bone marrow transplant.

For patients to be implanted with the SOPH-A-PORT Mini S IDDD the following conditions are contraindicated, as described in the Instructions for Use:

1. The patient has had, or may have, an allergic reaction to the materials of construction of the SOPH-A-PORT Mini S device
 2. The patient's body size is too small to support the size of the SOPH-A-PORT Mini S Access Port, as judged by the investigator
 3. The patient has a known or suspected local or general infection
 4. The patient is at risk of abnormal bleeding due to a medical condition or therapy
 5. The patient has one or more spinal abnormalities that could complicate safe implantation or fixation
 6. The patient has a functioning CSF shunt device
 7. The patient has shown an intolerance to an implanted device
-

6 STUDY TREATMENT(S)

6.1 Description of Treatment(s)

6.1.1 Study Drug

Recombinant human heparan N-sulfatase (HGT-1410 drug product) formulation is a sterile solution for injection in single-use vials for IT administration. It is formulated in an aqueous isotonic solution containing 15.0 mg/mL HGT-1410 in 145 mM sodium chloride, 0.02% (v/v) polysorbate 20, 5 mM sodium phosphate at pH 7.0.

6.1.2 Intrathecal Drug Delivery Device

The PORT-A-CATH will continue to be used for the administration of drug product for each patient until such time as an IDDD replacement may be required. Following implementation of protocol Amendment 4, any replacements will be performed using the SOPH-A-PORT Mini S.

After IDDD replacement the drug product will be administered via the SOPH-A-PORT Mini S Implantable Access Port. The SOPH-A-PORT Mini S device is intended for long-term, intermittent access to the IT space for the delivery of investigational drug.

The SOPH-A-PORT Mini S is comprised of the following 7 components:

- One SOPH-A-PORT Mini S Access Port
- One intrathecal port closed-tip catheter
- One guidewire
- Two suture wings
- One 14-gauge Tuohy needle
- One 22-gauge non-coring Huber needle
- One Luer lock Connector.

Further details are provided in the Instructions for Use.

